12.1.4 Reasons for Declining Study Participation

If a subject declines to participation in the study, he/she will be asked to provide a reason for declination which will be recorded in a screening log.

12.2

12.3 Secondary Study Outcome Measures

12.3.1 Patient Reported Toxicities

Patient reported toxicity data will be collected via Carevive surveys weekly for the first 12 weeks and then every other week for another 36 weeks. The questions will be from the PRO-CTCAE which is a patient-reported outcome measure developed to evaluate the toxicities that clinical trial subjects experience [10]. We will not deliver the PRO-CTCAE in its entirety but will specifically ask about the following common toxicities that are experienced with oral targeted therapy and immunotherapy: diarrhea, nausea, vomiting, fatigue, hand/foot syndrome, rash, abdominal pain, anorexia, mouth sores, cough and shortness of breath.

12.3.2 Clinician Reported Toxicities

Toxicities will also be formally assessed in-office every 3-4 months after commencement of a new targeted therapy/immunotherapy at routine follow-up visits. The clinician will assess several categories and rank them according to the CTCAE. The CTCAE are a set of criteria designed to standardize the adverse effects of cancer drugs for clinical trial purposes [26]. The categories chosen are common toxicities that occur with oral targeted therapy and immunotherapy: diarrhea, nausea, vomiting, fatigue, hand/foot syndrome, rash, abdominal pain, appetite, mouth sores, cough and shortness of breath

12.3.3 Quality of Life

Subjects will be asked to fill out the Functional Assessment of Cancer Therapy-Kidney Symptom Index (FKSI-DRS) at baseline and approximately every 3 months in-office on a tablet device, with the help of the study team if needed. The FKSI-DRS is a 15-item index of the most important symptoms and concerns of people with advanced kidney cancer which has been determined to be reliable and valid when used in this setting [27].

12.3.4 Distress Level

The subject will be asked to rate their distress level in-office using the NCCN Distress Thermometer and Problem List for Patients [28], which is a 1 to 10 numerical scale. This will be delivered during routine office visits approximately every 3 months on a tablet.

12.3.5 Drug Adherence

The subject's drug adherence will be measured in the monthly survey using a three-question scale, and will also be determined through the subject's medication refill history. The subject's medication refill history will be obtained through their electronic medical record at the end of the study or at time of withdrawal.

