2.3. Secondary Aim

2.3.1. Collect preliminary data on RCC patients' symptoms, health care utilization, quality of life, distress level and oral drug adherence while on targeted therapy or immunotherapy.

- To determine how patients' treatment-related toxicities correlate to their quality of life, distress level, drug adherence and health care utilization.

3.0.CHARACTERISTICS OF THE RESEARCH POPULATION

3.1 Number of Subjects: We expect to recruit 50 advanced renal cell carcinoma patients from the genitourinary oncology program at Wilmot Cancer Institute of the University of Rochester Medical Center over a one-year period.

3.2 Gender of Subjects: Both men and women will be enrolled in this study. Advanced RCC is known to be almost twice as prevalent in men than women [24], therefore we can expect a roughly 2:1 male to female enrollment rate.

3.3 Age of Subjects: We will recruit patients 18 years and older for this study, however RCC is very uncommon in patients <45 years of age and typically affects adults between the ages of 45 and 84 [1].

3.4 Racial and Ethnic Origin: This study has no enrollment restrictions based upon race or ethnic origin. RCC is known to be less prevalent in Asian and Pacific Islanders [1].

3.5 Inclusion Criteria:

- 3.5.1 Diagnosis of histologically confirmed renal cell carcinoma of any subtype with either pathological or radiographic evidence of metastatic disease
- 3.5.2 Greater than 18 years of age
- 3.5.3 A participating Wilmot Cancer Center oncologist has determined that candidate should be started on either oral targeted therapy or immunotherapy for treatment of their advanced RCC; this can be for first-line or any subsequent line therapy**
- 3.5.4 Able to provide written informed consent
- 3.5.5 Proficient in the English language and self-reports as literate
- 3.5.6 Must have an active email address or access to a smart device

3.6 Exclusion Criteria:

- 3.6.1 Women cannot be breast-feeding
- 3.6.2 Does not have regular access to the internet
- 3.6.3 Unable to come to the Wilmot Cancer Center for appointments every 3-4 months for routine visits with their primary oncologist
- 3.6.4 Subjects who were on the study previously will not be allowed to re-enroll in the event of a treatment change

3.7 Vulnerable Subjects: No special classes of subjects such as fetuses, neonates, children, pregnant women, prisoners, institutionalized individuals or other vulnerable populations will be recruited.

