6.0. METHODS AND STUDY PROCEDURES

6.1 Overview of Study:

We will conduct a phase II, single-arm clinical trial to assess the feasibility of reporting and managing side effects from oral targeted therapy or immunotherapy, through Carevive software, in patients who have advanced RCC. The study will begin when the consented subject starts a new therapy, either an oral targeted agent (pazopanib, sunitinib, axitinib, cabozantinib, lenvatinib, everolimus) or infusional immunotherapy (nivolumab), and will continue for a duration of 48 weeks or until drug is permanently discontinued by their primary oncologist. All study subjects will be asked to log their symptoms through Carevive software weekly for 12 weeks and then every other week for the next 36 weeks. Based on their symptoms, subjects will receive self-management instructions through the software (if applicable). Subjects will also be asked to monitor their medication compliance and health care utilization through the Carevive software once every four weeks for the length of the study. In addition, subjects will be asked to fill out a survey at their medical oncology office visits approximately every 3 months. This survey will include a distress assessment and a quality of life questionnaire. During these visits, a clinician will formally assess the subject's medication related adverse events. At the end of the study, the subject will be asked to fill out an in-office survey rating the usability of the Carevive software. On study completion, the subject's electronic medical record will be reviewed to determine health care utilization and oral targeted therapy refill history during the study period.

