15.0. DATA ANALYSIS AND MONITORING

15.1 Primary Outcomes:

Primary Aim 1: *To evaluate the feasibility and usability of symptom monitoring and management with Carevive software.* Specifically, we will determine the demand for this intervention by calculating the rate of compliance. For example, in the case of monthly compliance, the

proportion of subjects who log in at least once during this time frame will be reported. The threshold criteria for compliance based on previous studies [29-30], will be a monthly compliance of 75% (ie. during each month, an average of at least 75% of the subjects completed at least one Carevive survey). Compliance will be determined for both survey completion and access of generated care plans. A sample size of 50 subjects produces a two-sided 95% confidence interval with a width of 0.254 for a point estimate of 75% compliance. Separately patient-level compliance will be determined, based on the proportion of logins that the subject completed during the course of the study. Reasons for noncompliance will be elicited at their subsequent login and will be reported descriptively.

Patient-rated usability, based on their SUS survey results, will also be employed as a measure of feasibility. This survey will be administered to subjects at the end of the study. A Score of >68 indicates greater than average usability [25]. We will determine overall mean usability scores, and we can produce a 95% confidence interval for the mean with a width of 0.57 standard deviations, utilizing the sample of 50 subjects.

We will also determine potential implementation obstacles for Carevive software by asking patients who fail to consent to the study to provide their reasoning. This will be reported descriptively. We will also keep track of the proportion of patients who are approached who fail to consent.

15.2 Secondary Outcomes:

Primary Aim 2: *To determine how patient-reported toxicities correlate to the subject's quality of life, distress level, drug adherence, health care utilization and physician reported toxicities.* Grading of each symptom and numeric values for quality of life, distress level, drug adherence and health care utilization rate will be determined as described in the "Data Collection and Monitoring Section." The strength of the association between symptom grade and each outcome will be measured using the Spearman's rank correlation coefficient.

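### Refill adherence has no stated denominator and no planned capture of clinician-directed holds, so its correlation with toxicity can be biased negative by an amount between negligible and moderate

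*Combined protocol and SAP*

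**What the plan says.** Section 2.3.1 asks how toxicities "correlate to their quality of life, distress level, drug adherence and health care utilization".

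Section 12.3.5 provides two adherence measures. Adherence is "measured in the monthly survey using a three-question scale, and will also be determined through" refill history. The schedule table lists them as separate rows: patient-reported adherence every four weeks from week 4, and a pharmacy-confirmed measure at week 48 or treatment discontinuation. On the source of the refill data, section 12.3.5 says that "medication refill history will be obtained through their electronic medical record at the end of the study or at time of withdrawal". Section 6.1 gives the scope of the final review: the subject's "electronic medical record will be reviewed to determine health care utilization and oral targeted therapy refill history during the study period".

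Follow-up "will continue for a duration of 48 weeks or until drug is permanently discontinued by their primary oncologist" (section 6.1). Section 7.2 adds withdrawal at the discretion of study personnel. A temporary hold is not listed as ending follow-up.

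On analysis, section 15.2 says: "The strength of the association between symptom grade and each outcome will be measured using" Spearman's rank coefficient. No adjustment is stated. For the derivation of the adherence value, section 15.2 points back to the data collection section. Section 12.3.5 gives no formula, denominator or rule for interruptions.

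**The concern.** Refill history shows when drug was dispensed. It does not show whether a gap arose because the subject missed doses or because a clinician told the subject to stop for a time. Toxicity is a plausible reason for such an instruction. If held days stay in the observation window, the variable on one side of the correlation (symptom grade) acts directly on the other (refill coverage), whatever the subject's own behaviour.

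The error would run in one direction. A negative coefficient could be reported as toxicity reducing adherence when part or all of it reflects instructions that were followed. Later work that used these preliminary data to plan an adherence intervention would start from the wrong premise.

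Dose changes raise a related difficulty. How many days a dispensed supply covers depends on the dose prescribed at the time. Section 12.3.7 takes treatment types and doses from the record for the baseline forms only.

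**Working it through.** **Inputs from the plan.** The maximum window is 48 weeks × 7 = 336 days (section 6.1). Planned N is 50 (section 3.1). Nivolumab is infused, so the number of subjects with an oral refill record is below 50 by a share the plan does not give. The statistic is an unadjusted Spearman coefficient (section 15.2).

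**Figures to reproduce.** The plan states none for adherence or for this correlation. Its two precision figures concern compliance and usability, and both reproduce. An exact (Clopper-Pearson) interval at 37.5 of 50 has width 0.2542 (stated 0.254), and 2 × t(0.975, 49)/√50 = 0.568 SD (stated 0.57). Neither depends on adherence.

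**Step 1: effect of one hold.** Let T be days observed, h hold days, and a the share of non-held days that the subject covers. Ordinary coverage is C = a(T − h)/T. With a = 1 and h = 14:
- T = 336: 322/336 = 95.8%
- T = 168: 154/168 = 91.7%
- T = 84: 70/84 = 83.3%, which applies only to a subject observed for about 12 weeks

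With hold days removed from the denominator, C = a(T − h)/(T − h) = a, and the hold cancels.

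**Step 2: direction.** If hold frequency or length rises with symptom grade, average h rises with grade and C falls with it, even when a is unrelated to grade. If holds are unrelated to grade, no correlation arises.

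**Step 3: size.** The plan gives no hold rates, hold lengths or adherence spread, so all of these are assumptions. In every simulation a is independent of grade, so the true correlation is 0.

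*Setting A:* 40 oral-agent subjects; worst grade 0–3 with probabilities 0.20/0.35/0.25/0.20; holds of 14–28 days; beta-distributed a; 2,000 trials per row. Results agree to about 0.01 between runs.

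| Window | Mean (SD) of a | Hold probability, grade 3 vs lower | Mean rho |
|---|---|---|---|
| 168 days | 95% (0.03) | 30% vs 5% | -0.12 |
| 168 days | 95% (0.03) | 50% vs 5% | -0.21 |
| 168 days | 95% (0.03) | 70% vs 10% | -0.29 |
| 336 days | 85% (0.11) | 30% vs 5% | -0.04 |
| 336 days | 85% (0.11) | 50% vs 5% | -0.07 |
| 336 days | 85% (0.11) | 70% vs 10% | -0.09 |
| either | either | 10% vs 2% | -0.01 to -0.04 |

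The coefficient from a single trial has an SD of about 0.16 (1/√39). In the 336-day rows with hold probabilities of 30% to 70%, p < 0.05 occurs in 6–9% of trials.

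*Setting B:* 336 days, N = 50, mean adherence 90%, average hold 14, 28 or 56 days.
- Hold probability 0/5/15/40% by grade: mean rho -0.07, -0.11, -0.15; p < 0.05 in 8%, 12%, 18% of trials.
- Hold probability 0/10/30/70% by grade: mean rho -0.13, -0.20, -0.28; p < 0.05 in 15%, 29%, 52%.
- With N = 30, mean rho is about the same and p < 0.05 occurs in 7–12% and 10–34% of trials respectively.

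*Controls:* With hold days removed, mean rho is about 0 and p < 0.05 occurs in about 5% of trials. With a 30% hold probability at every grade, mean rho is also about 0.

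**The case against.** The best defence is that the plan makes no wrong statement here. Four points deserve weight.

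- **No metric is defined.** A reader might infer that the plan counts clinician-directed holds as non-adherence and so builds in the correlation it wants to estimate. The documents do not say that. The bias follows from the usual way of filling the silence, and only if holds depend on toxicity.
- **Refill history is not the only measure.** The self-report is collected alongside the symptom surveys, and section 15.2 does not say which measure enters the correlation. The three items are not shown, so nobody can say whether they separate holds from missed doses.
- **The chart stays open.** A reader might infer that the analyst could never separate holds from missed doses. That goes too far. The record is reviewed at the end (sections 6.1, 12.3.5, 12.3.6), and section 13.2 lists medications among the data that can be extracted. A documented hold remains retrievable. What is missing is a commitment to retrieve it.
- **The effect may be small.** Over the plan's full window, one 14-day hold costs 4.2 percentage points (14/336). A fall to 83% needs an 84-day window, which is not the plan's. With rare holds or widely varying adherence, the bias lies well inside sampling error.

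All four stand as limits on size and certainty. None supplies the missing denominator or hold dates.

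**Conclusion.** The gap is real. Adherence is to be correlated with symptom grade, refill history is one of its two sources, follow-up runs through temporary holds, and nothing in the plan defines the refill denominator or collects hold or dose-change dates. If an ordinary coverage measure is used and holds follow toxicity, the correlation is biased negative.

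The direction is secure under those two conditions. The size is not: with a true correlation of 0, mean rho runs from about -0.01 to about -0.29, depending on assumed hold rates, adherence spread and window. The plan supports no narrower range.

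The scope is limited to oral-agent subjects, one of two adherence measures, and a secondary aim that collects preliminary data. The compliance and usability outcomes and the sample-size justification are untouched. The change is worth making because it is cheap and removes a one-directional error. It is not a reason to doubt the feasibility result.

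**What to change.** 1. Add to the planned end-of-study record extraction (sections 6.1 and 12.3.5) the start and stop dates of documented clinician-directed holds and the dates of dose changes.
2. In section 15.2, define refill adherence for oral-agent subjects as days supplied divided by days on which the drug was prescribed, with documented hold days excluded.
3. Report the correlation with symptom grade separately for the refill and self-report measures.
4. Report time on hold as its own outcome, so that this consequence of toxicity is shown rather than absorbed into adherence.

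The cost is a few more fields in a chart review already planned and a short addition to section 15.2. Clinical management does not change. The remaining weakness is that undocumented holds would still be misclassified as non-adherence, which the report should state.

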12.3.6 Health Care Utilization

The subject's health care utilization will also be assessed by two measures. First, every four weeks via the Carevive survey, the subject will be asked about hospitalizations, emergency or urgent care visits, and unanticipated office visits to their primary care provider in the past month. At the end of the study or at time of withdrawal, a search of the electronic medical record will be performed to determine the number of calls made to oncology care providers and the number of visits to the oncologist.

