Immunotherapy is a new form of cancer treatment that has been found to be effective in a variety of cancer types over the last several years. In metastatic RCC, nivolumab, which is a monoclonal PD-

1 blocking antibody, was also approved in 2015 for second-line treatment based on an enhanced patient overall survival by 6 months [18]. Nivolumab works by blocking the interaction of PD-L1 on tumor cells and the PD-1 receptor on T cell surfaces, thereby activating the immune system against cancer cells. Nivolumab is delivered as an intravenous infusion every two weeks and is being prescribed with increasing frequency. Therefore, although it is not an orally available agent, it is prudent to include nivolumab in our study of side effect reporting and management since many metastatic RCC patients will receive this therapy at some point during the course of their treatment. The most common side effects experienced with nivolumab are fatigue, rash, diarrhea, anorexia, nausea, constipation, vomiting, cough and shortness of breath.

Given the overall side effects profiles of the TKIs, everolimus and nivolumab, we have chosen the following eleven common side effects for patient electronic reporting and self-management in this study: diarrhea, nausea, vomiting, fatigue, hand/foot syndrome, rash, abdominal pain, anorexia, mouth sores, cough and shortness of breath.

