6.6 In-Office Assessments (Week 12, 24, 36 and 48)

Every 3-4 months at routine visits, the physician will perform a toxicity check and will document the grade of the following CTCAE parameters in the subject’s electronic medical record: diarrhea, nausea, vomiting, fatigue, abdominal pain, rash, anorexia, weight loss, oral mucositis, cough and shortness of breath. The subject will again be asked to fill out a FKS-DRS quality of life survey and the “NCCN Distress Thermometer and Problem List for Patients” on a tablet or computer while they are in the office.

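### Counting every oncologist visit, with no allowance for drug class, can dilute or confound the oncologist-visit part of the toxicity–utilisation correlation

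*Combined protocol and SAP*

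**What the plan says.** Section 12.3.6 measures utilisation in two ways. The four-weekly survey asks about "hospitalizations, emergency or urgent care visits, and unanticipated office visits to their primary care provider in the past month". At the end of study or at withdrawal, a chart search is to "determine the number of calls made to oncology care providers and the number of visits to the oncologist". The restriction to unplanned contact is attached to primary care and not to oncology.

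Section 15.2 states: "The strength of the association between symptom grade and each outcome will be measured using the Spearman's rank correlation coefficient". No stratification or adjustment by drug is mentioned. The section refers to a utilisation rate, but gives neither its denominator nor a rule for combining the components.

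Section 6.1 enrols subjects on oral targeted agents and on nivolumab in one arm, for 48 weeks or until the drug is permanently stopped. Section 1.3 says "Nivolumab is delivered as an intravenous infusion every two weeks". Routine oncologist visits are described for everyone. Exclusion criterion 3.6.3 removes anyone "Unable to come to the Wilmot Cancer Center for appointments every 3-4 months for routine visits with their primary oncologist", and section 6.6, headed weeks 12, 24, 36 and 48, says "Every 3-4 months at routine visits, the physician will perform a toxicity check".

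**The concern.** The secondary aim in section 2.3 asks how toxicity relates to utilisation. For that, a visit count should reflect need for care. A count that includes scheduled attendances also reflects which drug the subject receives. If nivolumab subjects accumulate infusion attendances that are logged as oncologist visits, they rank high on visits whatever their symptoms.

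Two things can follow. With equal toxicity in the two classes, the schedule adds rank variation unrelated to symptoms, and a real correlation shrinks. If a symptom is also more or less common on nivolumab, drug class is linked to both variables and the pooled coefficient is confounded. Section 15.2 grades each symptom separately, and the side-effect lists in section 1.3 make a class difference plausible for some symptoms. Hand-foot syndrome and mouth sores are each listed for several oral agents and not for nivolumab.

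**Working it through.** **The plan's own figures.** None is stated for this correlation. The two precision figures in section 15.1 concern other outcomes, and both reproduce. An exact (Clopper-Pearson) interval at 37.5/50 has width 0.254. The usability mean gives 2 × t(0.975, 49)/√50 = 0.568 SD, stated as 0.57.

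**Visit counts over 48 weeks (documents).**
- Nivolumab infusions: 48/2 = 24.
- Routine visits for all subjects: 48/12 = 4 at the section 6.6 weeks, or 48/17.3 = 2.8 at four-month spacing.
- If every infusion counts and four coincide with routine visits, nivolumab subjects have 24 − 4 = 20 extra scheduled visits. If none counts, they have 0.

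**Assumptions (not in the documents).** N = 50, all followed for 48 weeks; nivolumab share f of 20–50%; 4 to 20 extra scheduled visits on nivolumab; unscheduled visits Poisson with mean 2 at average toxicity, log-slope 0 (no effect) or 0.4 per SD of toxicity (real effect); symptom shift on nivolumab of −0.5, 0 or +0.5 SD.

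**Simulated mean pooled rho, all visits counted.** The rows with 20 extra visits use 1,500 runs each.

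| Nivolumab share | Extra visits | Real effect, equal toxicity | Real effect, symptom 0.5 SD lower | No effect, 0.5 SD lower | No effect, 0.5 SD higher |
|---|---|---|---|---|---|
| 20% | 20 | 0.31 | 0.17 | −0.14 | 0.14 |
| 40% | 20 | 0.24 | 0.02 | −0.20 | 0.21 |
| 50% | 20 | 0.22 | 0.01 | −0.21 | 0.21 |
| 50% | 4 | 0.28 | 0.09 | −0.19 | – |

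Across the whole range of 20–50% and 4–20 extra visits, the results are 0.22 to 0.35 (real effect, equal toxicity), 0.00 to 0.23 (real effect, 0.5 SD lower) and −0.13 to −0.21 (no effect, 0.5 SD lower). With a real effect and the symptom 0.5 SD higher on nivolumab, the upward bias roughly offsets the dilution, and rho is about 0.44.

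**Comparators.** Counting unscheduled visits only gives about 0.47 with a real effect and about 0 with none. Adjusting for class gives 0.44–0.47 with a real effect. With no extra visits there is no distortion.

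**Hand check of the 20-visit rows.** When the two classes barely overlap on visits, a class making up a fraction q of subjects occupies a block of width qN in the visit ranks. Two approximations follow.

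1. *Dilution with equal toxicity:* pooled rho ≈ within-class rho × [f² + (1 − f)²]. With within-class rho 0.46:
   - f = 0.5: 0.46 × 0.50 = 0.23 (simulated 0.22)
   - f = 0.4: 0.46 × 0.52 = 0.24 (0.24)
   - f = 0.2: 0.46 × 0.68 = 0.31 (0.31)
2. *Confounding with no effect:* pooled rho ≈ 6f(1 − f)[Φ(shift/√2) − 0.5]. For a shift of −0.5, Φ(−0.354) = 0.362, so the bracket is −0.138:
   - f = 0.5: 1.50 × −0.138 = −0.21 (−0.21)
   - f = 0.4: 1.44 × −0.138 = −0.20 (−0.20)
   - f = 0.2: 0.96 × −0.138 = −0.13 (−0.14)

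The size therefore depends mainly on the drug mix and the symptom shift. Once the classes separate, further scheduled visits add little, which is why 4 extra visits already produce much of the effect.

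**The case against.** Several objections stand and limit the point.

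- **Infusions may not be oncologist visits.** Section 1.3 describes an infusion, not a consultation. If the chart search excludes infusion attendances, nothing is distorted. The text does not settle this, and the person abstracting the chart would have to decide.
- **No class difference in toxicity is quantified.** The documents give lists, not rates. Eight of the eleven surveyed symptoms are on nivolumab's own list; only hand/foot syndrome, abdominal pain and mouth sores are not. The lists also vary among oral agents: pazopanib's names neither hand-foot syndrome nor mouth sores. Without a class difference there is dilution but no false correlation.
- **The drug mix is unknown.** Section 1.1 says oral agents are the most commonly prescribed first-line treatment, and section 1.3 gives nivolumab's approval as second-line. A share nearer 20% than 50% is plausible, and effects are smaller there.
- **Only one component is exposed.** Hospitalisations, emergency or urgent care visits, unanticipated primary-care visits and calls are not fixed by an infusion schedule.
- **No test is planned.** Section 15.2 measures strength of association and states no alpha, so the harm is a misleading estimate rather than a wrong test decision.

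A reader might also infer three stronger claims that the documents do not support. The first is that the drug schedule drives the toxicity–utilisation correlation; that would need the counting rule, the drug mix and class-specific toxicity, none of which is given. The second is that the 3–4 month interval belongs to oral-drug subjects; criterion 3.6.3 and section 6.6 apply it to everyone, with infusions additional. The third is that refill adherence is wrongly applied to infused subjects; section 2.3 speaks of oral drug adherence and section 6.1 of refill history for oral targeted therapy, so that restriction is already present.

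**Conclusion.** The point holds as a conditional weakness in one secondary correlation. Scheduled and unplanned oncologist visits are not separated, and drug class is not accounted for. To the extent that infusion attendances are recorded as oncologist visits, the pooled coefficient can be roughly halved with equal toxicity (from about 0.47 to 0.22–0.35). For a symptom 0.5 SD less common on nivolumab, it can be nearly erased (0.00–0.23) or falsely negative when there is no effect (−0.13 to −0.21). A symptom more common on nivolumab biases it upward. These sizes rest on the assumed drug mix, symptom shift, visit counts and full 48-week follow-up.

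The aim is to collect preliminary data. The primary feasibility outcome and the sample of 50 are unaffected. This is a cheap improvement, not a flaw that threatens the study.

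**What to change.** **Section 12.3.6:** count unscheduled visits to the oncologist, excluding infusion attendances and the routine visits at weeks 12, 24, 36 and 48, and express the count per unit of follow-up because participation ends when the drug is stopped. This changes what is counted, not when subjects are seen.

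**Section 15.2:** report the utilisation correlations as a partial Spearman coefficient adjusted for drug class (oral targeted or nivolumab), or separately within class. The partial form is (r_sv − r_sc·r_vc)/√[(1 − r_sc²)(1 − r_vc²)], where s is symptom rank, v is utilisation rank and c is class. It may be the more practical choice: at a 20% share only 0.2 × 50 = 10 subjects would be on nivolumab, with a null standard error for rho of about 1/√9 = 0.33, against 1/√49 = 0.14 for all 50.

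**Cost:** a visit-type flag in a chart search that is already planned, a few words in two sections, fewer events counted and slightly wider intervals. No change to the adherence measure is needed on this account.
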